10.1 PROCEDURES FOR EVALUATING SUBJECT COMPLIANCE

The devices will not be handled by subjects.

At each visit, subjects will be questioned concerning the use of any topical or systemic prescription or other products. Subjects will also be questioned about prohibited activities such as sun exposure.

The investigator will instruct the subject of the importance of adhering to the protocol. If it can be proven that the subject is obviously not compliant, the investigator can decide to withdraw him from the study.

10.2 PROCEDURES FOR RECORDING, REPORTING AND ANALYSING CIP DEVIATIONS

All CIP deviations will be managed according to Eurofins Dermascan Pharmascan Standard Operating Procedure (SOP).

DERMOSCIENCES FRANCE	Medical Device CIP # 22E2387	Final version 1.0 Date: 16.08.2022	Confidential Page 39/49
-------------------------	---------------------------------	---------------------------------------	----------------------------

Deviations to the CIP should be classified as:

- **Minor** if they don't impact the rights, safety or well-being of the subjects. They do not increase the risk or do not diminish the benefit for the subject and/or do not have a significant effect on the integrity of the data collected,
- **Major (or CIP violations)** if they affect the rights, safety or well-being of participants. They increase the risk or diminish the benefit for the subject and/or have a significant effect on the integrity of the data in the study.
- **Critical:** if violations of the protocol as mentioned above that necessarily require suspension or closure of the study.

If a major deviation is reported/observed during the study, the investigator may decide to drop-out the subject of the study or not.

If the deviation is detected after the study end, the case will be discussed during the « data review » which occurs before data analysis.

10.3 NOTIFICATION REQUIREMENTS AND TIME FRAMES

Major deviations, in case of emergency, to protect the rights, safety and well-being of the subjects are reported to the sponsor and the EC as soon as possible according to Eurofins Dermascan Pharmascan SOPs. Minor deviations are reported to the sponsor and the EC at the study end.

10.4 CORRECTIVE AND PREVENTIVE ACTIONS AND PRINCIPAL INVESTIGATOR DISQUALIFICATION CRITERIA

If major deviations from the investigator is observed during the study, the CRA will warn the investigator of the importance to respect the CIP. An investigator who continuously violates the CIP despite CRA warnings could be excluded from the investigation with the approval of the sponsor.

11- DEVICE ACCOUNTABILITY

Investigational devices should only be dispensed under the supervision of the investigator or personnel approved for the study.

The device will be used only under conditions defined in this CIP and only for included subjects.

The CRO must keep an updated dispensation form which contain the subject number, the amount of MD dispensed to and returned at each visit, with the corresponding dates. This will be collected on a specific form.

All devices supplied as part of the investigation (empty containers, as well as used, partly used or unused devices) must be available for inspection at every monitoring visit. The CRA should verify the investigational site's devices accountability records against record of administrated doses in the source document. All MD (wasted and unused) will be destroyed accordind to Dermascan Poland procedures at the end of the study.

At study end, a reconciliation of MD supplies will be done by the CRO.

12- STATEMENTS OF COMPLIANCE

12.1 REGULATORY ASPECT

The study will be performed in accordance with:

- this CIP,
- the Good Clinical Practices (GCP)
- the EU regulation 2017/745 of 5 April 2017 and ISO 14155:2020 standard,
- the ethical principles that have their origin in the Declaration of Helsinki and its later modifications,

DERMOSCIENCES FRANCE	Medical Device CIP # 22E2387	Final version 1.0 Date: 16.08.2022	Confidential Page 40/49
-------------------------	---------------------------------	---------------------------------------	----------------------------

- the European Directive 2001/20/CE transposed in Polish Law (version of 07.08.2009, amended by the European Regulation # 596/2009 dated on June 18, 2009 - Dziennik Urzędowy, # L188, page 14).

This CIP will be submitted for opinion to an Ethics Committee (EC) and for authorization to the Polish competent authority (URPL).

12.2 ETHICS COMMITTEE

It is the responsibility of the sponsor or its legally designated representative to submit a copy of the CIP and of the detailed subject information sheet and consent form to an ethics committee in order to obtain independent approval before the conduct of the study.

The clinical investigation cannot begin until the favorable opinion of the ethics committee has been obtained. The approval of the ethics committee must be sent in writing, to the sponsor or its legally designated representative and then to the investigator. The EC approval letter must mention the members and their quality. Any additional requirements imposed by the EC must be met, if appropriate.

12.3 COMPETENT AUTHORITY (CA)

After receiving EC approval, the sponsor or its legally designated representative must address an authorization request the Polish competent authority (URPL).

It is the responsibility of the sponsor or its legally designated representative to submit a copy of the CIP and detailed information regarding investigational device to the competent authority. The clinical investigation cannot begin until the approval of the CA has been obtained when required. Any additional requirements imposed by the CA must be met, if appropriate.

12.4 INSURANCE

The sponsor has subscribed an insurance contract covering the cost of treatment of subjects in the event of clinical investigation related injuries, if applicable, the financial consequences of the liability of all investigators, the sponsor itself and anyone involved in the study.

The collaboration agreements are established by the sponsor.

The copy of the insurance certificate is presented separately in the EC submission file.

12.5 FINANCING OF THE CLINICAL INVESTIGATION

The clinical investigation is entirely financed by the sponsor. The sponsor is responsible for the clinical investigation funding in its totality including the investigators payment, subject's compensation and treatment of potential AE connected with the study product/procedures.

An agreement has been signed between the sponsor and the CRO (Eurofins Dermascan-Pharmascan).

The sponsor has delegated to the CRO the signature of the agreements with the clinical investigation sites and investigators.

13- INFORMED CONSENT PROCESS

13.1 GENERAL INFORMATION

Voluntary written informed consent form must be obtained from each subject prior to perform any study related procedures in compliance with the recommendations of the declaration of Helsinki. Subject should not be screened or included before the subject has signed an approved informed consent form, written in a language that is understandable to him.

The investigator, or delegates, will give both verbal and written information and explain the nature, purpose, and risks of the study. The subject will be informed that he has the right to withdraw at any time from the study, without giving reasons. The informed consent process must take place under conditions where the

subject has adequate time to consider the risks and benefits associated with his participation in the study. The informed consent form should be personally signed and dated in two originals by the subject and the person who conducted the informed consent discussion.

The investigator is responsible for ensuring the appropriate content of the informed consent form and that informed consent is obtained from each subject in accordance with all applicable regulations. The informed consent form will be reviewed and approved by the sponsor and the EC.

Each subject should receive one original of the signed and dated written informed consent form.

The second original of the signed and dated informed consent form should be retained in the investigator's file. The investigator should maintain a log of all subjects who signed the informed consent form.

No copy of this log will be given to the CRO nor the sponsor.

In the case of new information, requiring the signature of a new informed consent, the subjects will be informed as soon as possible.

13.2 PROCESS FOR SUBJECT'S INFORMATION AND CONSENT OBTAINING ON INVESTIGATIONAL SITE

A first information about the study aims and investigational device will be given by phone by the centre recruitment team (see section 6.3.5; phone call lasts approximately 15 minutes).

At screening visit (at least 24h before D0 visit), the investigator or delegates will again inform the subject about the study aims and constraints as well as the investigational device and will give him two paper copies of the informed consent form. After a reflexion time of 20 minutes on site and after all further questions are resolved, if the subject agrees to participate to the study, he will be asked to date and sign the informed consent in two original copies.

14- ADVERSE EVENTS, ADVERSE DEVICE EFFECTS AND DEVICE DEFICIENCIES

14.1 DEFINITIONS

Table below presents categorization of adverse events:

Adverse events	Non-device-related	Device- or investigational procedure-related	
Non-serious	Adverse Event (AE) ^a	Adverse Device Effect (ADE) ^c	
Serious	Serious Adverse Event (SAE) ^b	Serious Adverse Device Effect (SADE)	
		Anticipated	Unanticipated
		Anticipated Serious Adverse Device Effect (ASADE)	Unanticipated Serious Adverse Device Effect (USADE)

^a Includes all categories
^b Includes all categories that are serious
^c Includes all categories that are related to the device or the investigational procedure

14.1.1 Adverse event (AE)

Untoward medical occurrence, unintended disease or injury, or untoward clinical signs (including abnormal laboratory findings) in subjects, users or other persons, whether or not related to the investigational medical device and whether anticipated or unanticipated.

NOTE 1: This definition includes events related to the investigational medical device or the comparator.

NOTE 2: This definition includes events related to the procedures involved.

NOTE 3: For users or other persons, this definition is restricted to events related to the use of investigational medical devices or comparators.

14.1.2 Adverse device effect (ADE)

Adverse event related to the use of an investigational medical device.

NOTE 1: This definition includes adverse events resulting from insufficient or inadequate instructions for use, deployment, implantation, installation, or operation, or any malfunction of the investigational medical device.

NOTE 2: This definition includes any event resulting from use error or from intentional misuse of the investigational medical device.

NOTE 3: This includes 'comparator' if the comparator is a medical device.

14.1.3 Device deficiency

Inadequacy of a medical device with respect to its identity, quality, durability, reliability, usability, safety or performance.

NOTE 1: Device deficiencies include malfunctions, use errors and inadequacy in the information supplied by the manufacturer including labelling.

NOTE 2: This definition includes device deficiencies related to investigational medical device or the comparator.

14.1.4 Serious adverse event (SAE)

Adverse event that led to any of the following:

- a) death,
- b) serious deterioration in the health of the subject, that resulted in any of the following:
 1. life-threatening illness or injury,
 2. permanent impairment of a body structure or a body function,
 3. hospitalisation or prolongation of patient hospitalization,
 4. medical or surgical intervention to prevent life-threatening illness or injury or permanent impairment to a body structure or a body function,
 5. chronic disease,
- c) foetal distress, foetal death, or a congenital physical or mental impairment or birth defect.

NOTE 1: Planned hospitalization for a pre-existing condition, or a procedure required by the CIP, without serious deterioration in health, is not considered a serious adverse event.

14.1.5 Serious adverse device effect (SADE)

Adverse device effect that has resulted in any of the consequences characteristic of a serious adverse event.

14.1.6 Unanticipated Serious Adverse Device Effect (USADE)

Serious adverse device effect which by its nature, incidence, severity, or outcome has not been identified in the current risk assessment.

NOTE 1: anticipated serious adverse device effect (ASADE) is an effect which by its nature, incidence, severity, or outcome has been identified in the risk assessment.

14.1.7 Serious health threat

Signal from any adverse event or device deficiency that indicates an imminent risk of death or a serious deterioration in the health in subjects, users or other persons, and that requires prompt remedial action for other subjects, users or other persons.

NOTE 1: This would include events that are of significant and unexpected nature such that they become alarming as a potential serious health hazard or possibility of multiple deaths occurring at short intervals.

14.1.8 Severity definition

The severity of adverse events can be graded on a three-point scale:

- * **Mild:** Slight inconveniences, without any effects on the daily activities, no concomitant treatment taking.
- * **Moderate:** Some inconveniences, some effects on the daily activities and/or possibility to take concomitant treatment to resolve the event.
- * **Severe:** Big inconveniences having an impact on the daily activities and/or concomitant treatment necessary.

14.1.9 Relationship to the investigational device and investigation procedures

The relationship between the use of the medical device (including the medical/surgical procedures described in section 2.9) and the occurrence of each adverse event shall be assessed and categorized as described in the MDCG-2020-10/1 guidelines.

The relationship of each adverse event to the investigation procedures must also be assessed and categorized in the same way.

During causality assessment activity, clinical judgement shall be used and the relevant documents, such as the Investigator's Brochure, the CIP or the Risk Analysis Report shall be consulted, as all the foreseeable serious adverse events and the potential risks are listed and assessed there. The presence of confounding factors, such as concomitant treatments, the natural history of an underlying disease, other concurrent illness or risk factors shall also be considered.

Each AE will be classified according to four different levels of causality:

1. Not related
2. Possible
3. Probable
4. Causal relationship

The sponsor and the investigators will use the following definitions to assess the relationship of the adverse event to the investigational device or the investigation procedures.

1. **Not related:** Relationship to the device or procedures can be excluded when:
 - the event has no temporal relationship with the use of the device or investigation procedures;
 - the adverse event does not follow a known response pattern to the medical device (if the response pattern is previously known) and is biologically implausible;
 - the discontinuation of medical device application or the reduction of the level of activation/exposure - when clinically feasible - and reintroduction of its use (or increase of the level of activation/exposure), do not impact on the adverse event;
 - the event involves a body-site or an organ that cannot be affected by the device or procedures;

DERMOSCIENCES FRANCE	Medical Device CIP # 22E2387	Final version 1.0 Date: 16.08.2022	Confidential Page 44/49
-------------------------	---------------------------------	---------------------------------------	----------------------------

- the serious adverse event can be attributed to another cause (e.g. an underlying or concurrent illness/ clinical condition, an effect of another device, drug, treatment or other risk factors);
In order to establish the non-relatedness, not all the criteria listed above might be met at the same time, depending on the type of device/procedures and the adverse event.

2. **Possible:** The relationship with the use of the investigational device, or the relationship with procedures, is weak but cannot be ruled out completely. Alternative causes are also possible (e.g. an underlying or concurrent illness/ clinical condition or/and an effect of another device, drug or treatment). Cases where relatedness cannot be assessed, or no information has been obtained should also be classified as possible.
3. **Probable:** The relationship with the use of the investigational device, or the relationship with procedures, seems relevant and/or the event cannot be reasonably explained by another cause.
4. **Causal relationship:** the adverse event is associated with the investigational device or with procedures beyond reasonable doubt when:
 - the event is a known side effect of the product category the device belongs to or of similar devices and procedures;
 - the event has a temporal relationship with investigational device use/application or procedures;
 - the event involves a body-site or organ that
 - o the investigational device or procedures are applied to;
 - o the investigational device or procedures have an effect on;
 - the adverse event follows a known response pattern to the medical device (if the response pattern is previously known);
 - the discontinuation of medical device application (or reduction of the level of activation/exposure) and reintroduction of its use (or increase of the level of activation/exposure), impact on the adverse event (when clinically feasible);
 - other possible causes (e.g. an underlying or concurrent illness/ clinical condition or/and an effect of another device, drug or treatment) have been adequately ruled out;
 - harm to the subject is due to error in use;

In order to establish the relatedness, not all the criteria listed above might be met at the same time, depending on the type of device/procedures and the adverse event.

The sponsor and the investigators will distinguish between the adverse events related to the investigational device and those related to the procedures (any procedure specific to the clinical investigation). An adverse event can be related both to procedures and the investigational device.

Complications caused by concomitant treatments, not imposed by the clinical investigation plan, are considered not related. If routine procedures are not imposed by the clinical investigation plan, complications caused by them are also considered not related.

In some particular cases the event may not be adequately assessed because information is insufficient or contradictory and/or the data cannot be verified or supplemented. The sponsor and the investigators will make the maximum effort to define and categorize the event and avoid these situations. Where an investigator assessment is not available and/or the sponsor remains uncertain about classifying the adverse event, the sponsor should not exclude the relatedness; the event should be classified as "possible" and the reporting is not delayed.

Particular attention shall be given to the causality evaluation of unanticipated serious adverse events. The occurrence of unanticipated events related could suggest that the clinical investigation places subjects at increased risk of harm than was to be expected beforehand.

14.2 LIST OF NON-REPORTABLE ADVERSE EVENTS AND RATIONALE

Not applicable, all adverse events will be reported to the sponsor at the study end.

14.3 PROCESS FOR REPORTING ADVERSE EVENTS AND DEVICE DEFICIENCIES

14.3.1 Recording adverse events

The following must be assessed and recorded by the investigator in the subject's medical record in a timely manner and then transcribed onto the eCRF adverse event form at each visit:

- Observed or reported problems
- Complaints
- Physical signs and symptoms
- Medical condition which occurs during the study, having been absent at baseline
- Medical condition present at baseline, which appears to worsen during the study.

The need to capture AEs is not dependent upon whether or not the clinical event is associated with the use of the medical device.

Each recorded AE must be described as follows:

- Describe the event by stating the diagnosis (or symptoms), the underlying cause, coexisting disease, or other if identifiable. Whenever possible, the AE should be recorded unambiguously in standard medical terminology. In case the subject's complaint cannot be characterized, the subject's own words should be recorded.
- Note duration by entering the date of onset and date of resolution. If the event is present at the final study visit, indicate that the event is ongoing.
- Note the severity of the event: mild, moderate or severe according to provided definitions.
- Note the action taken as none, medical and/or surgical. Any prescribed medication must be noted in the subject's medical records and then transcribed onto the eCRF concomitant medication section. Surgical interventions should be specified.
- Note the relationship to the study device, or procedure using the guidelines described above.

Any subject withdrawn from the study due to an AE will be followed until the outcome of the event is determined. The investigator will prepare a complete written summary of the event and its outcome, in addition to recording the event on the eCRF AE form.

All other AEs will be followed through to the end of this study. Any AE that is related to the study device and unresolved at the end of the study will be followed by the investigator.

The following categories of AE outcomes will be recorded:

- Resolved
- Ongoing
- Unknown.

All AEs information is reported at the end of the study in the clinical report.

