6.2.1.2 Instructions for use

- 1 | CLEANSE

Cleanse the face using 4 pumps of Foamer 15, rinse and dry.

- 2 | PEEL APPLICATION

Pour 2.5 ml of Cyrstal Peel into a cup and apply to the face using 1 cotton bud. Apply with vertical and horizontal strokes across all areas. Always start by applying the product on the T-Zone, followed by the jawline and mouth, and finish with the cheeks. Apply up to 3 layers, waiting for 1 minute between each layer. Leave the last layer up to 5 minutes, whilst observing skin reaction. Rinse abundantly with water and dry the face. Remove immediately in case of intense reaction or pain.

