6.2.3.2 Rescue treatment(s)

In case of adverse device effect affecting subject well-being, the investigator is authorized to interrupt the use of the investigational device and prescribe to the subject a rescue treatment.

The adverse event will be recorded in the subject's eCRF and source document, including details on rescue medication.

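### The adverse-event codes in section 14.3.1 cannot show that a reaction led to the peel being removed or withheld, nor that an event ended with sequelae or death

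*Combined protocol and SAP*

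**What the plan says.** Section 14.3.1 sets the content of each adverse-event record: a description, onset and resolution dates, severity, action taken, and relationship to the device or procedure. For action the instruction is "Note the action taken as none, medical and/or surgical". The two sentences after it ask only for drug and surgery details, the first being "Any prescribed medication must be noted in the subject's medical records and then transcribed onto the eCRF concomitant medication section".

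The same section states "The following categories of AE outcomes will be recorded" and lists three: resolved, ongoing and unknown. It also directs "If the event is present at the final study visit, indicate that the event is ongoing".

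Elsewhere the plan foresees two actions with the device itself:
- Section 6.2.1.2, on applying the peel: "Remove immediately in case of intense reaction or pain".
- Section 6.2.3.2, on an adverse device effect: "the investigator is authorized to interrupt the use of the investigational device and prescribe to the subject a rescue treatment". The only treatment detail it then asks to be recorded is the rescue medication.

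Section 14.1.4 counts death and "permanent impairment of a body structure or a body function" among the criteria for a serious adverse event. Section 4.2 lists persistent redness and pigmentation disorder among the anticipated effects. On analysis, section 7.2.2 says only that adverse events will be analysed.

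**The concern.** For a peel applied by a dermatologist, whether a reaction caused a session to be cut short, postponed or dropped is one of the more informative tolerance facts. The plan foresees such actions, but its coding list has no place for them. Tolerance and adverse events are secondary endpoints (section 6.1.3.2), and section 5.1 sets out to verify that benefits outweigh risks. Section 3 says that no clinical investigation of this device has yet been done, so this study would supply the first clinical figures on how often a reaction interrupts treatment.

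With the codes as written, the adverse-event form could not supply that count. Nor could it separate a full recovery from one that leaves a mark.

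**Working it through.** The plan states no figure to reproduce. The check applies the written codes to plausible cases and then asks whether another record supplies what is missing.

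**Step 1. Apply the codes.**

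| Case | Action code | Outcome code | What is lost |
|---|---|---|---|
| A. Intense burning, peel removed at once, no drug, subject continues | none (by elimination) | resolved | early removal |
| B. Persistent redness, next session withheld, no drug, subject stays in the study | none (by elimination) | resolved or ongoing | omitted session |
| C. Acute reaction settles but leaves a mark | depends on treatment | resolved if the acute event is closed; ongoing if the mark is the same event and is present at D78 | sequelae, as distinct from full recovery or a fading reaction |
| D. Death | any | no matching code | fatal outcome in this field |

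For A and B, the code of no action follows by elimination. The plan does not define the medical category, but the only details it requests are prescribed drugs and surgery, so no action is the most natural choice.

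**Step 2. Look for the missing information elsewhere.**
- *Description and severity.* Section 14.3.1 does not ask the description to state device action, and section 8.2.3 plans no medical coding. The severity grades in section 14.1.8 rest on inconvenience, daily activities and concomitant treatment, not on device action.
- *Withdrawal.* The reason for withdrawal (section 6.3.4.2) and the written summary for withdrawal due to an adverse event (section 14.3.1) cover only subjects who leave. They do not reach A or B.
- *Device accountability.* Section 11 requires amounts dispensed and returned at each visit, with dates, checked against administered doses. This can reveal the omitted session in B, but nothing ties it to the event. It does not record contact time, so it need not reveal A.
- *Deviations.* An omitted session may be logged under section 10.2. Early removal need not be, because section 6.2.1.2 sets upper limits on layers and contact time rather than fixed values.
- *Local tolerance.* The score in section 6.4.3.1 is a four-level overall rating with no device-action component.
- *Serious events.* Deaths and permanent impairment in C or D meet section 14.1.4 and go through the notification and SAE form in section 14.3.3.

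**Step 3. Define the affected class.** It consists mainly of non-serious reactions, handled without drug or surgery, in subjects who remain in the study. For these, no required field links the event to what was done with the device.

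**Step 4. Scale.** The plan gives no rate for such events. Up to 33 subjects have three sessions each, so at most 33 × 3 = 99 sessions are exposed. One subject is 1/33 = 3.0% of those included, so a single case is visible in a percentage table.

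**The case against.** The strongest reply is that nothing is hidden. Every event keeps its description, dates, severity and causality. The listed endpoint is the number of adverse events, to which an event coded as no action contributes in full. The local tolerance rating does not use the action code. This stands, and it limits the loss to one attribute of a recorded event.

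The medical category is also undefined, so an investigator might use it for rinsing off or withholding a peel. Section 6.2.3.2 pairs interruption with a rescue treatment, which would be coded medical. Both points narrow the class. But if investigators may differ on the category, a reliable count is still impossible, and removal under section 6.2.1.2 implies no drug.

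Dose records, the 100% document review (section 6.5.3) and the deviation log can recover an omitted session. That is true, though not its link to the event.

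On outcomes, a mark present at D78 should be coded ongoing, and unresolved device-related events are followed after the study. Lasting damage is coded resolved only if the acute event is closed and the mark is not entered separately. That can happen under the written codes, but it is not what they direct.

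Finally, the eCRF form is not among the documents and may hold more fields. The plan does not require them.

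**Conclusion.** The gap is real and narrow. The plan foresees removal and interruption of the device but provides no adverse-event code for either, and its outcome list has no code for sequelae or death. The likely effect is that reactions managed only by removing or withholding the peel, in subjects who stay in the study, cannot be tabulated as leading to device interruption. The primary lesion-count analysis is unaffected.

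A reader might infer more: that the report would show better tolerance than occurred, or that deaths and lasting damage would be lost. The documents do not support this. The events remain in the count, the local tolerance score is independent of the action code, and serious cases have their own reporting route.

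The number of affected events cannot be estimated from the documents. The conclusion assumes that investigators read the medical category as treatment given, and that the eCRF holds only what the plan requires. The point merits a change before data collection, because the details may not be recoverable afterwards.

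**What to change.** - In section 14.3.1 and the eCRF adverse-event form, add a separate descriptive field for action with the investigational device: none / removed early / session postponed or omitted / permanently stopped. Keep the existing action field for treatment.
- Add two outcome codes: resolved with sequelae, and fatal.
- In section 7.2.2, state that the report gives the number and percentage of subjects in the safety population with an adverse event leading to each device action, and with sequelae.

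These changes record what was done; they set no rule on when to remove, withhold or stop the peel. The cost is one eCRF field, two codes and one table line, with no extra visits or procedures. The safety summary may look slightly less favourable.
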